## Appendix G: Operating Characteristics of Bayesian Logistic Regression Model (BLRM) with Escalation with overdose control (EWOC)

### 1. INTRODUCTION

This document provides the technical details of the methodology that will be used in the dose escalation part of Study DS6157-A-U101.

### 2. STATISTICAL MODELS AND DOSE RECOMMENDATION

In this study, the Bayesian logistic regression model (BLRM) along with Escalation With Overdose Control (EWOC) principle will be applied in dose escalation part to help guide the determination of the maximum tolerated dose (MTD) or the recommended dose for expansion (RDE) of DS-6157.

#### 2.1 Bayesian Logistic Regression Model

In this study, a 2-parameter Bayesian logistic regression model (BLRM), as defined below, will be used:

$$\text{logit}(\pi(d_i)) = \ln(\alpha) + \beta \ln(d_i/d^*), \quad \alpha > 0, \beta > 0$$

where  $\text{logit}(\pi(d_i)) = \ln(\pi(d_i)/(1 - \pi(d_i)))$ ,  $\pi(d_i)$  is the dose limiting toxicity (DLT) rate at  $i^{\text{th}}$  dose level  $d_i$ . Doses are rescaled as  $d_i/d^*$  with the reference dose  $d^* = 9.6 \text{ mg/kg}$ . As a consequence,  $\ln(\alpha)$  is equal to  $\text{logit}(\pi(d^*))$  at dose  $d^*$ . Note that for a dose equal to zero, the probability of toxicity is zero.

#### 2.2 Prior Specification for BLRM parameters

The Bayesian approach requires the specification of a prior distribution for the BLRM parameters. A minimally-informative bivariate normal prior for the model parameters ( $\alpha, \beta$ ) is obtained as follows:

- Based on extrapolation of nonclinical toxicology studies in monkeys, the MTD is projected to be greater than 9.6 mg/kg in humans (the highest nonseverely toxic dose [HNSTD] of monkeys is 30 mg/kg and assuming humans and monkeys are equally sensitive, the MTD is projected to be 9.7 mg/kg in humans). The median prior probabilities of DLT are set to be approximately 8.0% and 24.5% at 1.6 mg/kg (projected starting dose for dose escalation) and at 9.6 mg/kg, respectively.
- For the remaining doses, the prior medians of probability of DLT are assumed linear in log-dose on the logit-scale.
- Set  $\text{Prob}(\pi(d_1) \leq 0.25) = 0.90$  and  $\text{Prob}(\pi(d^*) \leq 0.4) = 0.70$ , which yields wide prior credible intervals (obtained from minimally informative Beta distributions), the optimal parameters of the bivariate normal distribution can be obtained using EAST (version 6.5, Cytel Inc.) with BLRM module as follows:

**Table 2.1: Prior parameters for bivariate normal distribution of model parameters**

Parameters	Means	Standard deviations	Correlation
$\ln(\alpha), \ln(\beta)$	(-1.125, -0.308)	(1.373, 0.778)	0

CONFIDENTIAL

**Table 2.2: Prior probabilities of under, targeted and over dosing (simulated from the prior in Table 2.1)**

Dose (mg/kg)	Prior probabilities of DLT rate in interval			Mean	SD	Percentile		
	0-0.16	0.16-0.33	0.33-1.0			2.5%	50.0%	97.5%
1.6	73.2%	14.5%	12.3%	13.0%	16.4%	0.0%	6.2%	58.7%
3.2	63.0%	19.9%	17.1%	17.5%	18.7%	0.2%	10.4%	67.1%
4.8	54.9%	21.6%	23.5%	21.1%	20.2%	0.6%	14.0%	73.9%
6.4	47.7%	24.1%	28.2%	24.4%	21.3%	1.1%	17.3%	77.3%
8.0	40.3%	28.0%	31.7%	27.3%	22.2%	1.5%	20.3%	81.3%
9.6	34.7%	27.7%	37.6%	30.1%	23.0%	2.1%	23.9%	84.0%

### 2.3 Dose Escalation Following EWOC Principle

Dose recommendation for the next cohort will be based on summaries of the posterior probability of DLT across the postulated dose range. After patients of each cohort complete DLT evaluation during Cycle 1, the joint posterior distribution of the BLRM parameters will be generated according to Bayes' theorem based on the likelihood function of the accumulated DLT data from Cycle 1 and the prior distribution.

Posterior probabilities of DLT rate at different dose levels will then be obtained from updated BLRM, and summarized for DLT rate in 4 different ranges:

- [0%, 16%] as DLT rate interval for 'under-dosing'
- (16%, 33%] as 'target' DLT rate interval
- (33%, 60%] as DLT rate interval for 'excessive toxicity'
- (60%, 100%] as DLT rate interval for 'unacceptable toxicity'

The dose level recommended for next dose cohort will be based on these probabilities according to the EWOC principle. The EWOC principle requires that the recommended dose for the next dose cohort is the one with:

- The highest posterior probability of the DLT rate in the target DLT rate range of (16%, 33%]
- Less than 25% of probability for DLT rate >33% (probability for excessive or unacceptable toxicity).

### 2.4 Dose Increment During Dose Escalation with EWOC

- The dose level increment must not be greater than 100% even if the model suggested a higher dose than 100% for next cohort

### 2.5 Stopping Rule for MTD Determination

For MTD (or RDE if MTD is not observed) determination, the following stopping rules will be implemented for the dose escalation phase:

*CONFIDENTIAL*

- At least 6 evaluable patients at MTD/RDE level with at least 15 evaluable patients in total enrolled in the dose-escalation phase, or
- At least 9 evaluable patients have been enrolled at a dose level which is the model's recommendation for the next dose cohort and for which the posterior probability of targeted DLT rate interval is at least 50%, or
- DLT assessment with at least 3 evaluable patients at the maximum tolerated dose level with 95% credible interval for posterior probability of DLT rate within (5%, 33%), or
- Initial dose level  $d_1$  is too toxic

### **3. HYPOTHETICAL SCENARIOS AND MODEL PERFORMANCE**

#### **3.1 Scenarios and Dose-escalation Recommendations**

The BLRM following the EWOC principle, together with dose increment rules and stopping rules as specified previously should make reasonable dose escalation recommendations during a dose escalation process based on the DLT outcome data. [Table 3.1](#) shows the recommended next dose in some scenarios for the first 4 dose levels using the prior parameters specified in [Table 2.1](#). These scenarios assume that the starting BLRM dose is 1.6 mg/kg and each cohort has at least 3 evaluable patients for the BLRM following the EWOC principle to estimate next highest admissible dose level for next cohort. These simulations were conducted using EAST.

**Table 3.1: Dose-escalation recommendations for various scenarios**

Scenario ID	Assessed doses (mg/kg)	No. DLT/No. patients	Dose (mg/kg) for next cohort recommended by BLRM following EWOC
1.1	1.6	0/3	3.2
1.2	1.6, 3.2	0/3, 0/3	6.4
1.3	1.6, 3.2, 6.4	0/3, 0/3, 0/3	9.6
1.4	1.6, 3.2, 6.4	0/3, 0/3, 1/3	8.0
1.5	1.6, 3.2, 6.4, 8.0	0/3, 0/3, 1/3, 0/3	9.6
1.6	1.6, 3.2, 6.4, 8.0	0/3, 0/3, 1/3, 1/3	6.4
1.7	1.6, 3.2, 6.4, 8.0	0/3, 0/3, 1/3, 2/3	4.8
1.8	1.6, 3.2, 6.4	0/3, 0/3, 2/3	4.8
1.9	1.6, 3.2, 6.4, 4.8	0/3, 0/3, 2/3, 0/3	6.4
1.10	1.6, 3.2, 6.4, 4.8	0/3, 0/3, 2/3, 1/3	4.8
1.11	1.6, 3.2, 6.4, 4.8	0/3, 0/3, 2/3, 2/3	1.6
1.12	1.6, 3.2, 6.4	0/3, 0/3, 3/3	3.2
1.13	1.6, 3.2	0/3, 1/3	4.8
1.14	1.6, 3.2, 4.8	0/3, 1/3, 0/3	8.0
1.15	1.6, 3.2, 4.8, 8.0	0/3, 1/3, 0/3, 0/3	9.6
1.16	1.6, 3.2, 4.8, 8.0	0/3, 1/3, 0/3, 1/3	6.4
1.17	1.6, 3.2, 4.8, 8.0	0/3, 1/3, 0/3, 2/3	4.8
1.18	1.6, 3.2, 4.8, 8.0	0/3, 1/3, 0/3, 3/3	3.2
1.19	1.6, 3.2, 4.8	0/3, 1/3, 1/3	4.8
1.20	1.6, 3.2, 4.8	0/3, 1/3, 2/3	1.6
1.21	1.6, 3.2, 4.8	0/3, 1/3, 3/3	< 1.6
1.22	1.6, 3.2	0/3, 2/3	1.6
1.23	1.6, 3.2, 1.6	0/3, 2/3, 0/3	3.2
1.24	1.6, 3.2, 1.6	0/3, 2/3, 1/3	1.6
1.25	1.6, 3.2	0/3, 3/3	<1.6
2.1	1.6	1/3	1.6
2.2	1.6, 1.6	1/3, 0/3	3.2
2.3	1.6, 1.6, 3.2	1/3, 0/3, 0/3	6.4
2.4	1.6, 1.6, 3.2	1/3, 0/3, 1/3	3.2
2.5	1.6, 1.6, 3.2	1/3, 0/3, 2/3	1.6
2.6	1.6, 1.6	1/3, 1/3	<1.6
3.1	1.6	2/3	<1.6

Output highlights:

- Scenarios 1.x show different dose escalation scenarios of observing 0/3 DLT at initial dose level. The BLRM will recommend escalating to next dose level.
- Scenarios 2.x show different dose escalation scenarios of observing 1/3 DLT at initial dose level. The BLRM will recommend staying at the same dose level.

CONFIDENTIAL

- Scenarios 1.21, 1.25, 2.6, and 3.1 are some scenarios which the BLRM will recommend to stop the trial and determine the initial dose is too toxic.

The above showed that the BLRM following the EWOC principle gives reasonable recommendations to guide dose escalation process under various situations.

As indicated in the protocol, the selection of the dose for next cohort of patients by clinical team is not solely based on BLRM recommendation, but on a clinical synthesis of all the relevant information on safety profile (both DLT and non-DLT information), PK/PD, and the BLRM recommendations.

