**Table 3.2: Assumptions for dose-DLT relationship**

Scenario ID	True DLT rate in each dose (mg/kg)					
	1.6	3.2	4.8	6.4	8.0	9.6
1	8.0%	12.6%	16.3%	19.4%	22.1%	24.5%
2	1.0%	4.0%	6.0%	10.0%	14.0%	18.0%
3	1.0%	6.0%	21.0%	39.0%	54.0%	66.0%
4	39.0%	49.0%	60.0%	67.0%	71.0%	74.0%

For each simulation, the following settings and assumptions were applied. These simulations were conducted using EAST (version 6.4).

- The sample size for each cohort: at least 3
- The maximum sample size in total: 39
- The dose with the highest posterior probability for the target toxicity among the doses with less than 25% of probability for the excessive or unacceptable toxicity was selected as the next dose level
- The doses were selected from provisional dose (1.6, 3.2, 4.8, 6.4, 8.0, and 9.6 mg/kg) and dose skip was allowed as long as dose increment does not exceed 100%
- The stopping rules as specified in Section 2.5 were applied.

Table 3.3 shows the average probability of selecting each dose as the MTD and the average sample size over the simulations for each scenario.

CONFIDENTIAL

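### Three of the 32 dose recommendations in Appendix G Table 3.1 (scenarios 1.6, 1.11 and 1.19) do not follow from the stated prior, model and dose-selection rule, and the plan gives no numerical precision for a hard 25% limit

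*Combined protocol and SAP*

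**What the plan says.** Appendix G Section 2.1 states that "a 2-parameter Bayesian logistic regression model (BLRM), as defined below, will be used", with reference dose 9.6 mg/kg. Table 2.1 gives the prior: ln(α) and ln(β) are normal with means -1.125 and -0.308, standard deviations 1.373 and 0.778, and correlation 0.

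Section 2.3 (and protocol Section 10.7.3) sets two conditions for the next dose: the greatest posterior probability that the DLT rate lies in (16%, 33%], and a probability below 25% that it exceeds 33%. Section 3.2 puts the same rule in one sentence: "The dose with the highest posterior probability for the target toxicity among the doses with less than 25% of probability" of excessive or unacceptable toxicity. Section 2.4 caps each increase at 100%.

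Table 3.1, titled "Dose-escalation recommendations for various scenarios", lists the resulting recommendation for 32 sets of DLT outcomes, run in EAST, and the text below it concludes that the recommendations are reasonable. Table 2.2 gives prior interval probabilities and is labelled as "simulated from the prior in Table 2.1". Protocol Section 10.6 names East 6.5 for implementing the BLRM; Appendix G Section 3.2 says its simulations used version 6.4. No place gives a number of draws, a burn-in, a seed or a Monte Carlo error.

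**The concern.** Table 3.1 is the plan's demonstration of how its escalation rule behaves. If a row does not follow from the stated rule, the table or the description of the rule is wrong, and a reader cannot tell which.

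The 25% limit is a hard threshold. It governs the recommendation at every escalation step (protocol Section 5.1.1) and the estimate of the MTD (Section 5.1.3). If the probability compared with it carries unreported numerical error, a dose close to the cut may be admitted in one run and rejected in the next on identical patient data.

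**Working it through.** **Inputs** (all from Appendix G): model, Section 2.1; prior, Table 2.1; rule, Section 2.3; cap, Section 2.4; doses 1.6, 3.2, 4.8, 6.4, 8.0 and 9.6 mg/kg, Section 3.2; DLT outcomes, Table 3.1.

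**Method.** For dose d, logit π(d) = ln(α) + β·ln(d/9.6). The posterior is proportional to the prior times the product over doses of π(d)^x · (1 - π(d))^(n - x), where x of n patients had a DLT. It was integrated on a fixed grid over ln(α) and ln(β), spanning ±7 prior standard deviations with 801 to 2,401 points per axis. The disputed probabilities are stable to about 0.02 points. The rule is then: keep doses with P(π > 33%) < 25% and no more than twice the current dose, and take the one with the largest P(16% < π ≤ 33%).

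**Reproducing the table.** 29 of 32 rows match, so the model and rule have been read as intended. Scenario 1.16 is an example: 6.4 mg/kg has P(>33%) = 15.6% and target probability 48.6%; 8.0 mg/kg has 24.3% and 48.5%. The rule returns 6.4, as tabulated.

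**The three rows that do not match.**

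| Scenario | Table dose (mg/kg) | P(>33%) / target at table dose | Rule returns (mg/kg) | P(>33%) / target at that dose |
|---|---|---|---|---|
| 1.6 | 6.4 | 13.7% / 47.2% | 8.0 | 24.7% / 48.2% |
| 1.11 | 1.6 | 7.4% / 34.0% | 3.2 | 23.3% / 51.8% |
| 1.19 | 4.8 | 25.1% / 47.4% (not admissible) | 3.2 | 13.0% / 43.6% |

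Distances from the 25% limit: in 1.6, 25 - 24.68 = 0.32 points; in 1.19, 25.13 - 25 = 0.13 points; in 1.11, 25 - 23.33 = 1.67 points.

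**Could another reading rescue the table?** None of those tried reproduces all 32 rows.

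- Taking the highest admissible dose (Section 3.1 words it that way) misses 1.6, 1.11, 1.16 and 1.19.
- Coding the bound as 1/3 instead of 33% recovers 1.19, but 1.6 and 1.11 still fail and 1.16 now fails.
- A limit of 24.5% misses 1.11 and 1.19; 26% misses 1.6 and 1.11; 23% misses 1.10 and 1.19.
- Moving the prior parameters within their rounding (16 combinations) leaves the same three rows.

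**What can be inferred about precision.** Only Table 2.2 bears on it. Exact prior target probabilities across the six doses are 15.7, 20.5, 23.6, 25.7, 26.8 and 27.0%; the table prints 14.5, 19.9, 21.6, 24.1, 28.0 and 27.7%. The largest gap is 23.6 - 21.6 = 2.0 points. If these gaps are sampling error, they fit about 1,650 draws (rough 95% range 600 to 3,200, treating doses as independent). The standard error at the cut is √(0.25 × 0.75 / N): 1.8 points at N = 600, 1.1 at 1,650 and 0.8 at 3,200.

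**Conditional on an assumed number of independent draws**, the chance that sampling noise alone gives the tabulated dose (400 replicates each) is:

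| Draws (assumed) | 1.6 | 1.11 | 1.19 |
|---|---|---|---|
| 1,000 | 51% | 12.5% | 49% |
| 2,000 | 47% | 3% | 46% |
| 5,000 | 33% | 0 of 400 | 40% |
| 10,000 | 21% | 0 of 400 | 39% |
| 50,000 | 3.5% | 0 of 400 | 30% |

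**The case against.** A reader might infer from Table 2.2 that the posterior is sampled too coarsely. The documents do not show this. Table 2.2 comes from the prior, nothing says that the same settings produced Table 3.1, and its 18 probabilities are not independent. Noise also explains 1.11 poorly: beyond about 2,000 draws it practically never yields the tabulated dose. A transcription slip or a different software setting is as plausible there.

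A reader might also infer that overdose control is not reproducible. That goes too far. In 1.6 and 1.11 the tabulated dose is lower than the rule returns and well inside the limit. Only 1.19 breaches it, by about 0.13 points. Scenario 1.16 is also sensitive to simulation error, but mainly through a near-tie in target probability between two doses that both satisfy the limit.

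Finally, the table is illustrative. Appendix G Section 3.1 says that the choice of dose does not rest on the model alone, and protocol Section 5.1.1 adds clinical review of overall safety. A margin of 0.13 points means little clinically under a minimally informative prior.

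These objections stand as limits on the claim. They do not make the three rows follow from the stated rule, and clinical judgement should start from a correct model output.

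**Conclusion.** Three of 32 rows in Table 3.1 are inconsistent with Appendix G Sections 2.1 to 2.4. Two give a dose below the one the rule returns; one gives a dose just over the stated limit. This rests on the printed prior parameters, the six-dose grid and the rule as worded, and it survives rounding of the prior.

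The cause is unknown. Sampling error is a natural candidate for 1.6 and 1.19, which lie within about 0.3 points of the cut, and a weak one for 1.11. Because the draw count, seed and Monte Carlo error are unstated, the flip rates above hold only for the draw counts assumed. What can be said is that a Monte Carlo implementation could return different doses on the same data in scenarios this close to the limit, and that the plan does not report enough to rule it out. It is an inexpensive correction worth making, not evidence that the escalation design fails.

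**What to change.** 1. At each dose decision, and for the MTD estimate, compute the two-parameter posterior by numerical integration, as the main calculation or as a check on EAST. If simulation alone is kept, state the number of draws, the seed and the Monte Carlo error of the probability compared with 25%.
2. Rerun Table 3.1, recording the software version and settings.
3. Reconcile scenarios 1.6, 1.11 and 1.19 with Appendix G Sections 2.2 to 2.4, and say whether the table or the description changes. Align the highest-admissible-dose wording in Section 3.1 with the rule in Section 2.3.

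The cost is seconds of computing and a corrected appendix table. No patient numbers, visits or design features change.

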### 3.2 Operating Characteristics of the BLRM

To investigate the operating characteristics of the BLRM following the EWOC principle, the probability that each dose is selected as MTD and the average number of patients allocated to each dose level were assessed via simulations. Four scenarios for the dose-DLT relationship were considered: 1) the scenario based on the assumptions used to determine prior, 2) all doses are safe and the highest dose has a true DLT rate of 18.0%, 3) toxicity increase rapidly with dose escalation and true MTD is between 4.8 and 6.4 mg/kg; 4) all doses show excessive or unacceptable toxicity (i.e. DLT rate > 0.33). Table 3.2 shows the detailed assumption for each scenario.

**Table 3.2: Assumptions for dose-DLT relationship**

Scenario ID	True DLT rate in each dose (mg/kg)					
	1.6	3.2	4.8	6.4	8.0	9.6
1	8.0%	12.6%	16.3%	19.4%	22.1%	24.5%
2	1.0%	4.0%	6.0%	10.0%	14.0%	18.0%
3	1.0%	6.0%	21.0%	39.0%	54.0%	66.0%
4	39.0%	49.0%	60.0%	67.0%	71.0%	74.0%

For each simulation, the following settings and assumptions were applied. These simulations were conducted using EAST (version 6.4).

- The sample size for each cohort: at least 3
- The maximum sample size in total: 39
- The dose with the highest posterior probability for the target toxicity among the doses with less than 25% of probability for the excessive or unacceptable toxicity was selected as the next dose level
- The doses were selected from provisional dose (1.6, 3.2, 4.8, 6.4, 8.0, and 9.6 mg/kg) and dose skip was allowed as long as dose increment does not exceed 100%
- The stopping rules as specified in Section 2.5 were applied.

Table 3.3 shows the average probability of selecting each dose as the MTD and the average sample size over the simulations for each scenario.

CONFIDENTIAL

**Table 3.3: Simulation results for each scenario**

Dose (mg/kg)		< 1.6 *	1.6	3.2	4.8	6.4	8.0	9.6	Total
Scenario 1	True DLT rate	—	8.0%	12.6%	16.3%	19.4%	22.1%	24.5%	—
	Selected as MTD	6.5%	2.2%	7.6%	10.6%	16.2%	10.3%	46.6%	—
	Average # of patients	—	3.9	3.5	1.8	3.2	2.0	3.4	17.8
	Average # of patients with DLTs	—	0.31	0.43	0.29	0.61	0.45	0.84	2.94
Scenario 2	True DLT rate	—	1.0%	4.0%	6.0%	10.0%	14.0%	18.0%	—
	Selected as MTD	0.0%	0.0%	0.4%	1.4%	6.0%	8.2%	84.0%	—
	Average # of patients	—	3.1	3.1	0.6	3.2	1.7	5.4	17.1
	Average # of patients with DLTs	—	0.03	0.12	0.03	0.32	0.23	0.98	1.72
Scenario 3	True DLT rate	—	1.0%	6.0%	21.0%	39.0%	54.0%	66.0%	—
	Selected as MTD	0.2%	0.6%	20.4%	42.5%	31.2%	2.7%	2.4%	—
	Average # of patients	—	3.3	4.4	4.1	4.3	2.1	1.0	19.2
	Average # of patients with DLTs	—	0.03	0.26	0.86	1.67	1.14	0.66	4.63
Scenario 4	True DLT rate	—	39.0%	49.0%	60.0%	67.0%	71.0%	74.0%	—
	Selected as MTD	86.9%	8.9%	3.7%	0.5%	0.1%	0.0%	0.0%	—
	Average # of patients	—	5.3	1.4	0.4	0.2	0.0	0.0	7.3
	Average # of patients with DLTs	—	2.04	0.70	0.25	0.10	0.03	0.01	3.14

\*During simulation, the initial dose (1.6 mg/kg) is considered too toxic.

The above showed that the BLRM with EWOC can give reasonable recommendations to guide dose escalation process under various situations.

**Appendix H: Instructions Related to COVID-19**

Due to the potential impact of coronavirus disease 2019 (COVID-19, due to severe acute respiratory syndrome coronavirus 2 [SARS CoV-2]), on patient safety, the Sponsor recommends the following dose modification and management plan for patients with confirmed or suspected COVID-19 while being treated with DS-6157a. Dose modifications will be based on the worst CTCAE grade. **Use CTCAE version 5.0 general grading criteria to evaluate COVID-19.** All dose modifications (discontinuation, interruptions or reductions) must be recorded on the AE and drug administration eCRFs.

**Dose modification criteria for suspected or confirmed COVID-19**

If COVID-19 infection is suspected, delay DS-6157a and rule out COVID-19 per local guidance.

- If COVID-19 is ruled out, follow dose modification and management guidance as outlined in [Table 2](#).
- If COVID-19 is confirmed or is still suspected after evaluation follow dose modification as outlined in Table 4 below and manage COVID-19 per local guidance until recovery of COVID-19. COVID-19 recovery is defined as no signs/symptoms of COVID-19, at least 1 negative real-time reverse transcription polymerase chain reaction (RT-PCR) test result, and nearly or completely resolved chest CT findings.
  - [If PCR testing is not available at the site, to be considered recovered from COVID-19, the patient must not have any sign/symptoms for at least 2 weeks, in addition to meeting the requirement for chest CT imaging]

**Table 4 COVID-19 Dose modification criteria**

COVID-19 Worst Toxicity NCI-CTCAE Version 5.0 Grade (unless otherwise specified)	Schedule Modification for DS-6157a
Grade 1	Resume study drug at the same dose a
Grade 2	Resume study drug at the same dose if chest CT findings are completely resolved a Reduce by 1 dose level if chest CT findings are nearly resolved
Grade 3	Reduce by 1 dose level if chest CT findings are completely resolved a Discontinue study drug if chest CT findings are not completely resolved
Grade 4	Discontinue study drug

COVID-19 = coronavirus 2019; CT = computed tomography

a Closely monitor signs/symptoms after resuming DS-6157a, initially with a phone call every 3 days for the first week, and then with a weekly phone call thereafter, for a total of 6 weeks.

CONFIDENTIAL

In addition to the recommendations outlined in [Table 4](#), Investigators may consider dose modifications of the study drug according to the patient's condition and after discussion with the study Medical Monitor or designee.

If an event is suspected to be drug-related ILD/pneumonitis, manage per protocol ILD/pneumonitis management guideline ([Table 2](#)).

### **Prior and Concomitant Medications - Prohibited Therapies/Products**

- Chloroquine or hydroxychloroquine;
  - Concomitant treatment is not allowed during the study treatment (Section [5.3.2](#)).
  - If treatment is absolutely required for COVID-19 DS-6157a must be interrupted.
  - If administered, then a washout period of more than 14 days is required before resumption of DS-6157a.

### **PK Assessment(s) if Chloroquine or Hydroxychloroquine is Administered**

Additional PK serum samples should be collected if chloroquine or hydroxychloroquine is administered for COVID-19 infection, at the time points specified in the [Assessment Schedule](#) if feasible. If possible, these PK samples should always be collected.

The chloroquine or hydroxychloroquine administration time and the exact time of blood sample collection for PK analysis must be recorded on the eCRF.

